15.3.3.4. Displays of Zarit Burden Interview (Zarit-22)

Items from the Zarit-22 questionnaire collected during previous versions of the protocol will be presented in a data listing.

16. SAFETY OUTCOMES

All outputs for safety outcomes will be based on the safety population.

There will be no statistical comparisons between the treatment groups for safety data, unless otherwise specified in the relevant sections. Descriptive statistics will be presented for anxiolytic or hypnotic medication taken since last visit.

Document:

\

Author:

Version Number:

Final 1.0

Version Date:

24FEB2020

Template No: CS_TP_BS016 Revision 4
Effective Date: 01Apr2016

Reference: CS_WI_BS005

16.1. ADVERSE EVENTS

Both adverse events (AEs) and pre-treatment events will be coded using MedDRA central coding dictionary, Version 18.1 or higher.

For all adverse events analysis, first dose of study medication is defined as the first dose during DB period and OL period respectively.

Adverse events are untoward medical occurrences that started at the same time of or after the first dose of study medication. Untoward medical occurrences that started between ICF and prior to the first dose of study medication are pre-treatment events, i.e. events collected at Visit 1, Visit 2 and Visit 3.

Whenever available, the time information should be accounted for in the derivation of adverse events vs. pre-treatment events. In the case where time isn't available, untoward medical occurrences that started on or after the day of the first dose of study medication will be considered adverse events; those that started before the day of the first dose of study medication will be considered pre-treatment.

For the purpose of statistical analysis, all AEs in the DB period which started on or after the first dose of DB period study medication and within 9 days after the last dose of DB period study medication (given that this is before the first dose of the OL period study medication for subjects entering into the OL period), or had a partial or missing start date such that it cannot be determined whether the adverse event is within the 9-day window, will be included in DB period AE table summaries. All AEs in the OL period which started on or after the first dose of OL period study medication and within 9 days after the last dose of OL period study medication, or had a partial or missing start date such that it cannot be determined whether the adverse event is within the 9-day window, will be included in OL period AE table summaries.

See APPENDIX 2 for handling of partial dates for adverse events. In the case where it is not possible to define an untoward medical occurrence as adverse event or pre-treatment event, it will be classified by the worst case, i.e. adverse event.

An overall summary of the incidence of adverse events for DB period, OL extension period within each of the categories described in the following sections will be provided as specified in the templates. This summary for DB period will also be repeated by the race, sex, age, number of prior hospitalizations for PDP, and duration of PDP subgroups. The overall incidence summary for DB period, OL extension period and overall period will also be provided for AEs related to study medication.

Listings for DB period, OL extension period will be provided for all AEs, AEs leading to discontinuation of study medication, AEs leading to discontinuation from the study, serious adverse events (SAE), and AEs leading to death. A listing for pre-treatment events will also be presented.

For incidence summaries, each subject will be counted only once within each SOC and PT. If not otherwise specified, all summaries will present incidence (number of subjects and percentages) and number of events.

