The analysis of efficacy will be based on the modified Intent-to-Treat (mITT) population, which includes all subjects who are randomized, have received at least one dose of study drug, and have a Baseline and at least one post-Baseline efficacy measurement. The analysis of safety assessments will use the Safety population, which includes all subjects who are randomized and have received at least one dose of study drug.

The primary efficacy variable is the change from baseline in SAPS-PD score at Week 6 during the DB period for testing superiority of SEP-363856 to placebo. A Mixed Model for Repeated Measures (MMRM) will be used for this comparison. The MMRM model will include factors for treatment, visit (as a categorical variable), and treatment-by-visit interaction, and include baseline SAPS-PD score as a covariate. An unstructured covariance matrix will be used for the within-subject correlation and the Kenward-Rogers approximation will be used to calculate the denominator degree of freedom.

The secondary efficacy variables including change from baseline in CGI-S scores at Week 6, as well as change from baseline in NPI score and MMSE at Week 6 and will be analyzed similarly.

Descriptive statistics of observed values and changes from DB baseline and OL baseline in SAPS-PD, CGI-S score, NPI total score, MMSE total score, SCOPA-NS and SCOPA-DS total scores, and RBDQ total score will be summarized by visit.

Safety data including AEs, laboratory values, clinical evaluations, and C-SSRS will be summarized by treatment group overall and by study period (DB treatment period, open-label extension period). Adverse events, AEs leading to discontinuation, and serious AEs will be summarized by presenting, for each treatment group, the number and percentage of subjects with any AE, and AEs by system organ class and preferred term. Adverse events will be further summarized by severity and by relationship to study drug. The summary of AEs will include any AE occurring on or after the first dose of study drug.

Sample Size:

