12.4.1. Serious Adverse Event

If the Investigator or study center staff becomes aware of a SAE that occurs in a study subject after first administration of study drug through 30 days following the last dose of the study drug, this must be reported immediately to the Sponsor whether considered related or unrelated to the study drug. SAEs must be recorded on the CRF and the data recorded should agree with that on the SAE form. In addition, pretreatment events that meet the definition of serious (Section 12.1.2) should be reported following the same guidelines.

Following the end of subject participation in the study, the Investigator or an authorized delegate should report SAEs "spontaneously" to PPD-pharmacovigilance (PVG) if considered at least possibly related to the study drug.

SAEs will be followed until resolution, loss to follow-up, stabilization of condition, or the event is otherwise explained.

An initial or follow-up SAE form as applicable must be completed and signed and sent via fax or email (see Table 1) to PPD-PVG within 24 hours of the Investigator or study center staff

becoming aware of the event. The SAE form must be signed by the Investigator or appropriate designee. PPD-PVG provides the SAE form used to report SAEs.

The Sponsor or designee will promptly notify all study centers and Investigators of an SAE that is determined to be expedited to the Regulatory Authorities in accordance with applicable law(s) and regulation(s). These SAEs must be promptly reported to the Institutional Review Board (IRB) or Independent Ethics Committee (IEC) by the Investigator or the appropriate person at the study center if required per IRB/IEC guidelines.

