16.1.5. ADVERSE EVENTS LEADING TO DEATH

AEs leading to death are those AEs which are recorded as having an outcome of “Fatal” on the AE CRF page. A summary of AEs leading to death by SOC and PT will be prepared for DB period and OL extension period. A listing of deaths will be presented for DB period and OL extension period.

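### SAEs and fatal AEs that begin 10 to 30 days after the last dose are collected under the protocol but left out of the SAP's double-blind and open-label SAE and death tables

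*SAP*

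**What the plan says.** **Table window.** SAP 16.1 sets which events enter the AE tables. For the double-blind (DB) period an event must start on or after the first DB dose and "within 9 days after the last dose of DB period study medication", and before the first open-label (OL) dose for subjects who continue. For the OL period the limit is "within 9 days after the last dose of OL period study medication". Otherwise an event enters only if it "had a partial or missing start date such that it cannot be determined whether the adverse event is within the 9-day window". There is no exception for serious or fatal events.

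**SAE and death tables.** SAP 16.1.4 takes SAEs from the AEs flagged serious and tabulates them by period. SAP 16.1.5 takes deaths from the AEs with a fatal outcome: "A summary of AEs leading to death by SOC and PT will be prepared for DB period and OL extension period". Neither section gives its own time limit.

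**Collection.** Protocol 12.4.1 covers SAEs "after first administration of study drug through 30 days following the last dose of the study drug", whether or not related, and adds that "SAEs must be recorded on the CRF".

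**Protocol summary rule.** The Synopsis (Statistical Methods) states: "The summary of AEs will include any AE occurring on or after the first dose of study drug". Protocol 15.3.6.1 likewise sets a lower bound, for the OL period too, and no upper one.

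**Declared changes.** SAP 3.7 reports no departure from the protocol's analysis.

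**The concern.** The protocol sets a longer collection period for serious events than for ordinary ones, and the SAP then applies a single short window to both. Part of what sites must report never reaches the tables built to summarise it, and the SAP does not say so.

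The serious-event tables matter in this trial. Protocol 7.3.2 says the drug has not been given before to patients with Parkinson's disease or its psychosis. Protocol 7.3.1 says there are no data at age 65 or over. SAP 4.1 plans no data monitoring committee, so these tables are the main planned aggregate view of serious harm. Protocol 4.1 describes excess mortality with antipsychotics in elderly patients and an imbalance in serious events, including death, with the approved treatment. Those are other agents, and Protocol 4.3 describes a different mechanism for this one. They show what a safety reader will look for, not what to expect of this drug.

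In the DB comparison the gap reaches only subjects who stop without entering OL. If stopping differs between arms, the omission could also differ between arms.

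**Working it through.** **1. Where the 9 days comes from.** The SAP gives no derivation. Protocol 10.5.1 (Table 7) and 11.9.10 place the follow-up visit 7 ± 2 days after the last dose, so its latest day is 7 + 2 = 9. This matches the SAP's limit and is the likely source, though that is an inference.

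The match is not exact. Protocol 13.2 times follow-up from the last visit. With the last dose on Day 126 and Visit 13 on Day 127 (Protocol 11.9.9), follow-up could fall as late as 127 + 9 = Day 136, which is 136 − 126 = 10 days after the last dose.

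**2. The two windows compared.**
- SAE reporting: 30 days after the last dose.
- SAE and fatal-AE tables: 9 days after the last dose.
- Difference: 30 − 9 = 21 days (Days 10 to 30), and 21/30 = 70% of the post-dose reporting days. This is a share of calendar time, not of events.

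**3. Which events are lost.** The SAP tests the start date.
- Onset by Day 9, death on Day 20: stays in the tables.
- Onset on Day 15, known date, serious or fatal: on the CRF, but outside the DB and OL AE, SAE and death tables.
- Onset date too incomplete to place: stays in.

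**4. Which subjects are affected.**
- Subjects who continue: the first OL dose is at Visit 7 (Day 43), and the last DB dose is on Day 42. The OL window opens at once, so nothing is lost at the end of DB.
- Subjects who stop DB without entering OL: affected after their last DB dose.
- Everyone who enters OL, completers included: affected after the last OL dose.

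Each treated subject therefore passes through one uncovered interval, after the final dose. With about 36 randomized, 36 is the upper bound.

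**5. Weight of one event in a DB table.** With 24 and 12 subjects per arm, one omitted subject changes incidence by 1/24 = 4.2 percentage points on SEP-363856 or 1/12 = 8.3 on placebo. These denominators apply only to the DB tables. The OL tables use the OL extension safety population, whose size is not known in advance.

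**6. Chance that it matters at all.** The documents give no rate of late SAEs. Let p be an assumed risk per subject of SAE onset on Days 10 to 30. With 36 subjects, the expected number affected is 36p and the chance of at least one is 1 − (1 − p)^36.

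| Assumed p | Expected subjects | Chance of at least one |
|---|---|---|
| 1% | 0.4 | 30% |
| 2% | 0.7 | 52% |
| 5% | 1.8 | 84% |
| 10% | 3.6 | 98% |

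These values of p are illustrations, not estimates.

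**The case against.** **The window matches scheduled ascertainment.** Nine days is about when the follow-up visit closes, and Protocol 12.3 collects AEs to the last study visit. After that, SAEs arrive only if the site becomes aware of them. Protocol 12.4.1 also asks that SAEs arising after participation ends be reported if at least possibly related, so late unrelated events may be captured unevenly. Restricting incidence tables to the scheduled period is defensible. This stands for non-serious AEs. For SAEs it justifies a footnote, but it does not justify omitting events the protocol requires on the CRF.

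**The listings will show them.** This largely stands. The 9-day rule is worded for table summaries, listings of all AEs, SAEs and deaths are planned, and SAP Appendix 2 classes any event from first dose onward as a study AE with no upper limit. With about 36 subjects a reader could find late events there. But the listings are organised by period, the SAP does not say to which period a late event belongs, and listings give no incidence.

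**The protocol does not forbid a limit.** It states a lower bound and is silent on an upper one. That is fair, but its wording takes in any AE after first dose, so a cut-off narrows it and should be declared.

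**Stronger readings the documents do not support.**
- A reader might infer that any death on Days 10 to 30 disappears. The test is onset, so only fatal events that begin in that interval are lost.
- A reader might infer that a late event appears in no output at all. The listings remain. SAP 16.1 also plans an overall-period summary of related AEs, which the 9-day sentence does not mention, and the table templates are not in these documents.
- A reader might infer that the loss falls mainly on early stoppers. Every OL completer is exposed to it as well.
- A reader might infer that 70% of late SAEs are lost, or that the reported counts will be too low. The first confuses days with events. The second needs a late event to occur.

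**Conclusion.** The mismatch is real and limited in reach. As written, the SAP leaves SAEs and fatal AEs with a known onset on Days 10 to 30 after the last dose out of the DB and OL SAE and death tables, although the protocol requires them to be collected, and SAP 3.7 does not declare the restriction. The uncovered interval is 21 of 30 post-dose reporting days. It applies to subjects who stop DB without continuing and to all subjects after their last OL dose.

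This conclusion assumes that SAP 16.1.4 and 16.1.5 take their events from the AEs admitted by 16.1. That is the natural reading, since neither section sets its own window. The number of events affected cannot be derived from the documents. In arms of 24 and 12, a single one would be visible in a DB table. The point concerns the completeness of the safety tables and does not touch the efficacy analysis. It is worth correcting because the remedy is small.

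**What to change.** In SAP 16.1:
- Keep the 9-day window for non-serious AEs.
- For the SAE and fatal-AE tables, include events with onset from the first dose of the period through 30 days after its last dose, stopping before the first OL dose for subjects who continue. Alternatively, leave the present tables as they are and add one separate table of SAEs and deaths with onset after the 9-day window.
- State that the AE, SAE and death listings have no upper cut-off, and say to which period a late event is assigned.

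In SAP 3.7, declare the 9-day rule as a change from the protocol's AE summary.

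Footnote the wider tables to say that, after the follow-up visit, SAEs are not ascertained at scheduled visits, so the later days are less completely observed. That is the main drawback of the longer window.

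The cost is a few sentences in the SAP, one additional inclusion flag in programming and a footnote. No new data are needed, because these events must already be on the CRF. The change should be made before the double-blind data are unblinded.

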11.4.1. Adverse Events

Pretreatment events will be collected for each subject at Visits 1 and 2 (ie, prior to first dose administration).

Adverse events will be collected for each subject. Subjects should be queried in a non-leading manner, without specific prompting (eg, "Has there been any change in your health status since your last visit?"). See Section 12, Safety Reporting.

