APPENDIX 2. PARTIAL DATE CONVENTIONS

Imputed dates will not be presented in the listings. In the algorithms for date, 361-203 study med start date the date of first dose of study medication during double blind period.

ALGORITHM FOR ADVERSE EVENTS:

The concept of "date" below should also include time information whenever available.

START DATE	STOP DATE	ACTION
Known	Known	If start date < 361-203 study med start date, then pre-treatment events If start date >= 361-203 study med start date, then 361-203 AE
Known	Partial	If start date < 361-203 study med start date, then pre-treatment events If start date >= 361-203 study med start date, then 361-203 AE
Known	Missing	If start date < 361-203 study med start date, then pre-treatment events If start date >= 361-203 study med start date, then 361-203 AE
Partial, but known components show that it cannot be on or after 361-203 study med start date	Known	Pre-treatment events
Partial, but known components show that it cannot be on or after 361-203 study med start date	Partial	Pre-treatment events
Partial, but known components show that it cannot be on or after 361-203 study med start date	Missing	Pre-treatment events

Document:

\

Author:

Version Number:

Final 1.0

Version Date:

24FEB2020

Template No: CS_TP_BS016 Revision 4
Effective Date: 01Apr2016

Reference: CS_WI_BS005

START DATE	STOP DATE	ACTION
Partial	Partial	
Impute stop date as latest possible date (i.e. last day of month if day unknown or 31st December if day and month are unknown).
 
Then:
 
If stop date < 361-203 study med start date, then pre-treatment events
 
If stop date >= 361-203 study med start date, then 361-203 AE

Partial, could be on or after 361-203 study med start date	Known	
If stop date < 361-203 study med start date, then pre-treatment events
 
If stop date >= 361-203 study med start date, then 361-203 AE

Partial, could be on or after 361-203 study med start date	Partial	
Impute stop date as latest possible date (i.e. last day of month if day unknown or 31st December if day and month are unknown).
 
Then:
 
If stop date < 361-203 study med start date, then pre-treatment events
 
If stop date >= 361-203 study med start date, then 361-203 AE

Partial	Missing	Assumed 361-203 AE
Missing	Known	
If stop date < 361-203 study med start date, then pre-treatment events
 
If stop date >= 361-203 study med start date, then 361-203 AE

 Document:

\

Author:

Version Number:

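### SAP 16.1 has no tie-break for adverse events with incomplete start dates, so an event that cannot be placed is counted in both the double-blind and the open-label tables

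*SAP*

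**What the plan says.** SAP 16.1 defines the two sets of adverse event (AE) tables in parallel sentences.

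- **DB tables.** They take "all AEs in the DB period which started on or after the first dose of DB period study medication" and no later than 9 days after the last DB dose. A qualifier, "given that this is before the first dose of the OL period study medication for subjects entering into the OL period", closes that window at the first OL dose for anyone who rolls over. The alternative route in is an event that "had a partial or missing start date such that it cannot be determined whether the adverse event is within the 9-day window". Events entering by either route "will be included in DB period AE table summaries".
- **OL tables.** The rule opens: "All AEs in the OL period which started on or after the first dose of OL period study medication and within 9 days after". Its reference point for those 9 days is the final OL dose. The same alternative for incomplete start dates follows, and these events "will be included in OL period AE table summaries".

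For partial dates, 16.1 refers to Appendix 2, which fixes its reference point as follows: "In the algorithms for date, 361-203 study med start date the date of first dose of study medication during double blind period". Each branch of its AE algorithm ends in one of two outcomes, a pre-treatment event or a study AE. The worst-case sentence in 16.1 settles that same question and no other.

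SAP 5.8 labels DB safety results by the treatment actually received, placebo or SEP-363856. Protocol 15.3.6.1 restricts the OL summary to events on or after the first OL dose. SAP 3.7 states that the analysis does not change from the protocol.

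**The concern.** For a subject who stops during the DB period the clause is harmless, because there is only one treatment period in which to place the event. For a subject who rolls over, the DB and OL windows meet at the first OL dose. An event with no start date, or with only the month known when that month contains Visit 7, can satisfy both clauses at once.

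Two errors can follow. An event that began on open-label SEP-363856 can be shown in the DB table under the subject's DB treatment, which for some subjects is Placebo. An event that began during the DB period, including on placebo, can be shown in the OL table, where every subject is on SEP-363856.

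The DB table is the randomized comparison of adverse events, in the first study of this drug in Parkinson's disease (Protocol 7.3.2), with a placebo arm of about 12. If the SAP does not settle the allocation, it will be settled in programming, possibly after the DB unblinding that Protocol 15.3.10 schedules at the DB lock.

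**Working it through.** The plan states no figure for this, so there is nothing to reproduce. The check is a literal reading followed by context figures.

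**Reading the rules for a rollover subject**

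1. Start date missing, stop date missing or after the first OL dose. DB membership cannot be determined, so the DB clause includes the event. OL membership cannot be determined, so the OL clause includes it too. Appendix 2 returns only that it is a study AE. Result: both tables.
2. Start month known, day missing, and the month contains the first OL dose. The result is the same unless the stop date falls before that dose.
3. Start month known and lying wholly on one side of the first OL dose. The period is determined and there is no problem.
4. OL table against the protocol. In cases 1 and 2 the SAP admits events that may have begun before the first OL dose. Protocol 15.3.6.1 does not. Its own provision for missing dates decides only whether something is an AE.

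**Weight of one event**

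Inputs: 24 SEP-363856 and 12 placebo subjects (SAP 3.4); common-AE table at 5% or more in either group (SAP 16.1.1).

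- Placebo: 1/12 = 8.3 percentage points, so a single case reaches the 5% threshold.
- SEP-363856: 1/24 = 4.2 points, so a single case does not.

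**Where unplaceable onsets would truly lie**

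Assumptions: the subject completes both periods (42 and 84 days) and onset is equally likely on any day.

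- No date at all: 84/(42 + 84) = 67% of onsets are OL. With the 9-day tail after the last dose, 93/(42 + 93) = 69%.
- Day missing, month known: I simulated 20,000 completers with first doses spread evenly over a calendar year and five onsets each (100,000 onsets, 9-day tail included). About 22% fell in the month containing the first OL dose and could not be placed. About half of those were truly OL.

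**Does the misplacement favour one arm?**

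Illustrative assumptions, none from the documents: 10 of 12 placebo and 20 of 24 SEP-363856 subjects roll over, each has 3 OL events, and a fraction q = 0.01 to 0.05 of events cannot be placed. The chance that a subject carries at least one such event is 1 − exp(−3q), which is 0.030 to 0.139.

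- Placebo: 10 × (0.030 to 0.139)/12 = 2.5 to 11.6 points.
- SEP-363856: 20 × (0.030 to 0.139)/24 = 2.5 to 11.6 points.

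The expected addition is the same in both arms, so the expected shift in the risk difference is zero. These are upper limits. A subject counts once per term, so the any-AE rate rises only if the subject had no DB event. At the same event rate, 6 weeks would bring 1.5 events, and exp(−1.5) = 0.22 of subjects would have none. The placebo figure for any AE then falls to about 0.5 to 2.6 points. A single term would move by the full amount only if every misplaced event shared that term.

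**The case against.** The strongest defence is that the opening words of each sentence already limit it to events of that period. On this view the clause on incomplete dates only decides whether an event lies in the 9-day tail. SAP 16.1 also says that first dose means the first dose of each period respectively. That reading is possible, but neither document says how an event without a usable start date is assigned to a period in the first place, and Appendix 2 carries no OL date with which to do it.

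Several practical limits stand:

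- The DB tables are produced at the DB lock (Protocol 15.3.10, SAP 4), so OL events reported later cannot enter them. OL events of early enrollees could already be in the database, and no data cut is stated.
- Contacts are dense around the transition: Visit 7, calls on the next two days, then weekly visits to Visit 11 (Protocol 10.5.1 and 11.9.11). Unplaceable onsets there should be uncommon.
- All AEs are listed, and with about 36 subjects each doubtful event can be inspected.

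A reader might infer two stronger claims. The first is that such events go to the DB table by default. They do not: the OL sentence has the same clause, and the literal result is both tables. The second is that the rule favours the drug by inflating the placebo rate. The clause acts on both arms, and twice as many SEP-363856 subjects are available to contribute an event. A ratio could be pulled toward one, and chance or a different OL event rate in former placebo subjects could produce a net shift, but the documents give no figure that would show its direction.

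**Conclusion.** The gap is real. As written, SAP 16.1 counts an unplaceable AE of a rollover subject in both periods. It can show an event that began on open-label SEP-363856 in the DB column of either arm, including Placebo, and its OL half goes beyond what Protocol 15.3.6.1 allows.

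The consequence is double counting and a blurred DB comparison, not a demonstrated directional bias. One event is worth at most 8.3 points on a placebo term and 4.2 on a SEP-363856 term, at the planned arm sizes. How many events are affected cannot be estimated, because the documents do not say how often start dates are incomplete; it is probably few. The conclusion rests on a literal reading of 16.1 and would fall away if a period-assignment rule exists outside these two documents.

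**What to change.** Add the date of the first OL dose to Appendix 2 as a second anchor, and state in 16.1 that each AE is counted in exactly one period. Where the start date is incomplete, decide in this order:

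1. the known parts of the start date;
2. the stop date (a stop before the first OL dose means DB);
3. the visit or telephone contact at which the event was first reported, if the AE form captures it, which the documents do not show.

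The third step is reasonable because AEs are asked about at every visit, with a model question, "Has there been any change in your health status since your last visit", that ties the answer to the interval between visits (Protocol 11.4.1).

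Flag any event still unresolved in the listing, and repeat the DB overall AE table without those events. Make the change before the DB unblinding.

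The cost is a short SAP edit and minor programming. The one drawback is that a DB event reported late could be placed in OL; the flag and the repeat table would show it.
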